An anonymized copy on CD ROM (present in each observation book) of each morphological evaluation until progression (even if beyond 6 months) (MRI) is to be made. The copies will be sent to the CRGA of the FFCD for centralized review .

For the translational study, perform a cone beam CT acquisition or a hepatic CT scan without injection at the time of the 1^{ère} HEC.

For the clinical study, if possible, perform a cone beam CT acquisition at each HEC to assess the quality of the chemoembolization.

VII.3 Post-treatment monitoring beyond 6 months after inclusion:

After the end of chemoembolization treatment, patients will be followed according to TNCD recommendations:

Clinical and biological evaluation every 3 months for the first year and then every 6 months for 1 year:

- Clinical examination (weight, WHO)
- Biological tests: liver tests (ASAT, ALAT, GGT, bilirubinemia, albuminemia, TP)
- Marker : AFP

Morphological assessment:

- Chest CT scan without injection, every 6 months for 2 years
- Hepatic MRI (or CT scan) - liver ultrasound by a trained operator alternating every 3 months for 2 years

Monitoring data will be collected in the observation book during this 2-year period.

VIII. STOP PROCESSING THE STUDY

The processing of the study will be stopped in case of:

- Investigator's decision
- Major toxicity requiring discontinuation of treatment
- Serious or unexpected event requiring discontinuation of protocol treatment
- Progression of the disease
- Patient refusal or withdrawal of consent
- Death of the patient

In all cases of treatment discontinuation, the patient remains in the analysis for intention-to-treat and overall survival, and for 30 days after the last study treatment for toxicity.

There is no exclusion period for a subsequent therapeutic trial.

IX. TRANSLATIONAL STUDY

Only patients who have signed their translational-biological informed consent will be collected. Rationale for the study (see Appendix 15).

Blood sampling for VEGF determination

- 4 sampling times:

After the 1^{ière} HEC at D0, D1, D2 and D3

- Samples :

At each sampling time (4 times), collect 2 x 7 ml EDTA tubes of blood.

Centrifuge the blood tubes at room temperature at 1000 g for 15 minutes.

Collect the plasma to be distributed in a minimum of 4 cryotubes (minimum 1 mL per cryotube).

Identify the cryotubes with the patient's initials + inclusion number in the study, the sampling times.

Freeze the 2 plasma cryotubes at -20°C then at -80°C.

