Note: The time between collection and freezing (at -20°C) of plasma should not exceed 1 hour.

Complete the sample census form (present in the study investigator's binder) and send it by [contact]) or by email ([contact]) to the FFCD as soon as the 4 sampling times have been completed.

The repatriation of the samples to the CRB (biological resource center) EPIGENETEC of the FFCD, will be done at the end of the study by a specialized carrier.

Imaging for correlation with VEGF assay

Perform a cone beam CT or CT scan without injection after the 1^{ière} HEC.

An anonymized copy should be sent to the FFCD. A blank CD ROM is provided in the patient's CRF.

X. CENTRALIZED READING OF MRI AND CT

Responses will be evaluated according to the mRECIST version 1.1 (primary endpoint) and EASL (secondary endpoint) criteria (Appendices 4 and 5) and will be reviewed by a panel of independent radiologists who will confirm responses and dates of tumor progression or recurrence once all study examinations have been retrieved.

For this purpose, an **anonymized copy on CD ROM** (present in each observation book) **of each morphological evaluation until progression** (even if beyond 6 months) (MRI) is to be made. **The copies will be sent to the CRGA of the FFCD for centralized review.**

XI. MANAGEMENT OF SERIOUS ADVERSE EVENTS (SIA)

1. Security assessment parameters

Safety will be assessed by evaluating the general and clinical condition of patients and by collecting events occurring between visits during consultations. Toxicities will be assessed using the NCI-CTC-AE version 4.0 toxicity scale (see Appendix 6).

In case of an emergency, the patient, his family or his physician should call the investigator to warn of an event.

2. Definitions

a. Adverse Event (AE)

An adverse event is a harmful occurrence in a person who is a subject of biomedical research, whether or not the occurrence is related to the research or the product being investigated.

All adverse events will be recorded in the observation book on the pages provided.

b. Serious Adverse Event (SAE)

A serious adverse event (SAE) is considered to be any event:

- Resulting in death,
- Life-threatening,
- Leading to hospitalization or prolonged hospitalization,
- Causing permanent disability or severe temporary incapacity,
- Causing a birth defect, fetal malformation or abortion,
- Medically significant.

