If it is a serious unexpected adverse reaction, or if it is a new fact, the sponsor writes an initial report which will be transmitted to the ANSM, the CPP and the EMA (via EudraVigilance) within 7 days in case of death, otherwise within 15 days.

If it is an expected serious adverse event, it will be collected for the semi-annual and annual safety reports.

4. Modalities and duration of follow-up of individuals following the occurrence of adverse events.

The investigator is responsible for appropriate medical follow-up of patients until resolution or stabilization of the effect or until the patient's death. This may sometimes mean that this follow-up extends beyond the patient's discharge from the trial.

He/she transmits the additional information to the sponsor using an SAE reporting form (checking the Follow-up No. X box to specify that it is a follow-up report and not an initial report) within 24 hours of obtaining it. It also forwards the last follow-up to the resolution or stabilization of the SAE.

He keeps the documents concerning the suspected adverse reaction in order to allow, if necessary, to complete the information previously transmitted.

It responds to requests for additional information to document the initial observation.

XII. STATISTICAL ANALYSIS

XII.1 Provisional timetable for the study

With an expected rate of one patient per month per center, i.e. 10 patients per month, and with a suspension of inclusions between stage 1 and 2, the study schedule will be as follows:

Stage 1: 43 evaluable patients

- Expected start date of inclusion (stage 1): September 2014
- Anticipated end date of inclusion stage 1: February 2015
- Judging criterion at 6 months: August 2015
- Stage 1 analysis (+ 6 months): February 2016

Stage 2: 43 evaluable patients

- Expected start date of inclusion: February 2016
- Expected completion date of inclusion stage 2: July 2016
- Judging criterion at 6 months: January 2017
- Final analysis of primary endpoint (+ 6 months): July 2017
- 2-year overall survival analysis: January 2020

XII.2 Judging criteria

XII.2.1 Main criterion

The primary endpoint is the rate of patients with objective response (complete response or partial response) **at 6 months after inclusion** according to mRECIST criteria and centralized review.

XII.2.2 Secondary Criteria

The secondary endpoints of this study are:

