- The rate of patients in objective response** (complete response or partial response) at 6 months according to mRECIST criteria and evaluated by the investigator.
- The rate of patients in objective response** (complete response or partial response) at 6 months according to EASL criteria assessed by the investigator and in centralized review.

- Time to treatment failure

It is defined as the time interval between the date of inclusion and the date of protocol treatment failure. Death, progression, and any discontinuation of protocol treatment (regardless of cause) are considered treatment failures.

Patients alive without failure will be censored at the date of the last 6-month morphological evaluation.

- The best response according to the mRECIST criteria

- Progression-free survival

It is defined as the time interval between the date of inclusion and the date of 1st progression according to mRECIST criteria (assessed in centralized review) or death (regardless of cause).

Patients living without progression will be censored at the date of last news.

- Overall survival

It is defined as the time interval between the date of inclusion and the date of death (regardless of cause) or the date of last news for living patients.

- Tolerance of the treatment

Toxicities will be evaluated by the NCI-CTC v4.0 criteria. They will be described according to their grade in terms of number of toxicities and number of patients who experienced the toxicity.

- Quality of life (QLQ-C30 questionnaires and its HCC18 module specific to HCC)

XII.3 Calculation of the number of subjects needed

The assumptions are:

- H0: A proportion of patients with an objective response at 6 months of 25% or less is not acceptable
- H1: A proportion of patients with an objective response at 6 months of more than 25% would demonstrate the effectiveness of the treatment. A rate of 40% is hoped for.

Using a 2-stage Fleming design (Fleming, 1982) with a one-sided alpha risk of 5% and power of 90%, it is necessary to include **86 treated and evaluable patients**.

At the 1^{ère} stage: 43 patients will be included

- If 10 or fewer patients have an objective response, the trial will be stopped for futility (H1 rejection)
- If 18 or more patients have an objective response, the trial will be stopped for efficacy (rejection of H0)

If not, we will go to 2^{ème} step including 43 additional patients

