## 4.6 Test steps

### 4.6.1 First stage: interim analysis

An interim analysis was performed in January 2017 after inclusion of 46 patients (44 evaluable for the primary endpoint). At this stage, out of 44 evaluable patients, according to the decision rules, 19 or more patients needed an objective response at 6M to judge the treatment effective.

22 patients met this criterion and the treatment was therefore deemed effective. The trial was therefore stopped for efficacy (rejection of H0).

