## 7.3 Evaluation of primary endpoint efficacy

#### Population CP

### 7.3.1 Definition of primary efficacy endpoint

The primary endpoint is the objective response rate 6 months after inclusion. Objective response (complete and partial response) is defined according to mRECIST criteria and based on centralized review (or on the investigator's opinion if review is not possible).

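### Read literally, Protocol X has the panel confirm responses after the stage 1 decision that depends on them, and no section schedules a stage 1 central read

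*Protocol*

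**What the plan says.** **Endpoint.** Protocol XII.2.1 defines the primary endpoint as objective response 6 months after inclusion "according to mRECIST criteria and centralized review". Investigator-assessed response is a separate secondary endpoint (XII.2.2).

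**Stage 1 rule.** Protocol XII.3 applies counts of responders among 43 patients: 10 or fewer stops for futility, and at the upper end "If 18 or more patients have an objective response, the trial will be stopped for efficacy (rejection of H0").

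**Timing of the central read.** Section X sends responses to a panel of independent radiologists "who will confirm responses and dates of tumor progression or recurrence once all study examinations have been retrieved". Sections VII.2 and X ask for an anonymized copy "of each morphological evaluation until progression (even if beyond 6 months) (MRI) is to be made". Imaging after month 6 is described in VII.3: "Hepatic MRI (or CT scan) - liver ultrasound by a trained operator alternating every 3 months for 2 years".

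**Timetable.** XII.1 suspends inclusions between the stages. It puts the last stage 1 six-month assessment in August 2015, followed by "Stage 1 analysis (+ 6 months): February 2016". The last stage 2 six-month assessment is January 2017. No step for central reading is listed.

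**SAP.** Section 7.3.1 bases the primary endpoint on centralized review "or on the investigator's opinion if review is not possible". Section 4.3 states that the trial is open-label. Section 4.6.1 reports 46 patients included, 44 evaluable for the primary endpoint, and an adapted boundary of 19: "22 patients met this criterion and the treatment was therefore deemed effective". The trial then stopped for efficacy. The reader behind the 22 is not named.

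**The concern.** The stage 1 boundaries can be applied to the primary endpoint only once the central read exists for the stage 1 patients. Section X, the one place that dates this read, ties it to retrieval of all examinations, which on its plain wording comes later than the stage 1 analysis. The two instructions cannot both be followed literally, and the documents do not say which gives way.

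SAP 7.3.1 adds a route by which the gap could be filled with investigator reads. It does not define when review counts as not possible, and it does not ask for the number of such cases. A read that is simply not yet available at the interim could be treated as one of them.

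At stake is the decision that ended enrolment at 46 of 91 planned patients. If some or all of the count were investigator reads, the boundary would have been applied partly or wholly to what the protocol lists as a secondary endpoint, in an open-label single-arm trial. A later central count below the boundary would arrive with enrolment already closed.

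**Working it through.** **1. The plan's own figures reproduce.** Inputs from Protocol XII.3: p0 = 0.25, p1 = 0.40, one-sided alpha 5%, power 90%, n1 = 43, N = 86.

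Fleming rejection bound: the nearest integer to n·p0 + 1.645·√(N·p0·(1 − p0)), plus 1. The second term is 1.645·√(86 × 0.25 × 0.75) = 6.61.
- Stage 1, n = 43: 10.75 + 6.61 = 17.36, giving 17 + 1 = 18.
- Final, n = 86: 21.50 + 6.61 = 28.11, giving 28 + 1 = 29.
- Adapted stage 1, n = 44: 11.00 + 6.61 = 17.61, giving 18 + 1 = 19, as in SAP 4.6.1.

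The exact binomial calculation for bounds 10/18/29 gives alpha 0.047 and power 0.902. Inclusions: 86/0.95 = 90.5, rounded up to 91. The design figures are not in question. The question is which read feeds the bound.

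**2. Timing on the literal wording (planned dates, XII.1 and VII.3).**
- Stage 1 analysis: February 2016.
- Last stage 2 six-month assessment: January 2017, 11 months later.
- Last stage 1 patient included February 2015. Two years of imaging end in February 2017 if counted from inclusion (12 months after the stage 1 analysis), or in August 2017 if counted from month 6 (18 months after).

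Whether "all" is taken over the whole trial or over the full follow-up of stage 1 patients, the examinations cannot all be in hand at stage 1. If "all" means the examinations needed for the stage 1 endpoint, they are complete in August 2015, 6 months before the analysis.

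**3. Margin of the reported result (SAP 4.6.1).** 22/44 = 50.0%. A net loss of 3 gives 19, which still meets the bound. A net loss of 4 (4/22 = 18.2% of responders) gives 18, below 19 and above the futility range, so the rule would be to continue to stage 2.

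Exact one-sided 95% lower limits, by the SAP 7.3.2 method and with no adjustment for two stages: 36.8% at 22/44, 28.4% at 18/44, 26.3% at 17/44.

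**4. Sensitivity to reader disagreement.** The documents give no discordance rate, so both tables rest on assumed values.

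(a) All 22 are investigator reads. Each is downgraded at central review independently with probability q, and none is upgraded. Expected central count = 22(1 − q). Chance of falling below 19 = P(Bin(22, q) ≥ 4).

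| q | Expected count | Chance below 19 |
|---|---|---|
| 5% | 20.9 | 2% |
| 10% | 19.8 | 17% |
| 15% | 18.7 | 42% |
| 20% | 17.6 | 67% |
| 25% | 16.5 | 84% |

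(b) The true central rate is 25%, and investigators call a share f of non-responders responders. Observed rate = 0.25 + 0.75f. Chance of a stage 1 efficacy stop = P(Bin(n, rate) ≥ bound).

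| f | Rate | ≥18/43 | ≥19/44 |
|---|---|---|---|
| 0% | 25.0% | 1.1% | 0.6% |
| 5% | 28.75% | 4.5% | 2.9% |
| 10% | 32.5% | 12.6% | 9.0% |
| 15% | 36.25% | 26.9% | 21.1% |

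Both tables treat every read as an investigator read. A few fallback cases would have a smaller effect.

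**The case against.** Section X does not forbid an earlier read, and it does not say whether "all" is per patient, per stage or per trial. A stage-by-stage reading fits the rest of the plan: inclusions are suspended, 6 months separate the last stage 1 assessment from the analysis, and copies of each evaluation are to be sent for review. Scans beyond 6 months serve progression dating, and their absence does not make the 6-month scan unavailable. All of this stands. It shows that a stage 1 central read was feasible, not that the plan calls for one.

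A reader might infer that the trial was in fact stopped on investigator reads and that the stop was therefore invalid. The documents do not support this. SAP 4.6.1 calls the 44 patients evaluable for the primary endpoint and applies the decision rules to them, and SAP 7.3.1 defines that endpoint by central review, with a fallback. The reader is unnamed, but silence is not evidence of an investigator count.

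Nor would a lower central count show that the treatment failed. At 18/44 the rule leads to stage 2, and the single-stage lower limit of 28.4% still exceeds 25%. The downgrade range in the working is assumed, and it ignores upgrades.

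Finally, the final analysis reports both the primary endpoint rate and the investigator rate (SAP 7.3 and 7.4.1), so disagreement should become visible. That helps, but neither section asks for the interim count to be traced to its reader, and the primary rate may itself include fallback reads.

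**Conclusion.** The point holds as an internal conflict and a risk to the stop/continue decision. Section X's timing clause, on its literal reading, places confirmation 11 months or more after the planned start of the decision it should inform. No section schedules a stage 1 central read, and the SAP opens a route for open-label reads without limiting or counting it.

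The size depends on something the documents do not report. If the 22 were central reads, the reported result is unaffected and only wording needs repair. If they were investigator reads, 4 or more net downgrades (18% of responders) would have turned the stop into a continuation. How likely that is depends wholly on an assumed discordance: 2% at 5% downgrading, 84% at 25%. The sample size and boundaries are sound and need no change. An invalid stop has not been shown.

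**What to change.** **Protocol X.** Replace the timing clause. The panel reads the baseline and 6-month examinations of all stage 1 patients before the stage 1 analysis, and the XII.3 boundaries are applied to that read. Progression and recurrence dates may be read later. Enrolment has closed, so for this trial the change serves to put the intended rule on record.

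**SAP 4.6.1.** State which read produced 22/44 and how many of the responses relied on the investigator fallback in 7.3.1. If it was not the central read, apply the 19/44 boundary to the centrally read responses of the same 44 patients and report that as the basis for the conclusion.

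**Cost.** The same panel reads the same scans, in two batches instead of one. The stage 1 analysis might be delayed slightly, within the 6 months that XII.1 already allots. If the interim count was centrally read, one sentence in the SAP, with the fallback count, settles the reported result.

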Non-inclusion criteria	
 - Advanced tumor disease (vascular or extrahepatic invasion including brain metastases or diffuse HCC with $>$ 50% liver invasion) - History of other cancers excluding cancers known to be cured for more than 3 years (in this case histological evidence of HCC is required), or basal cell skin tumors or cervical cancer in situ adequately treated with curative intent - Previous treatment with idarubicin and/or doxorubicin - Contraindication to idarubicin (heart disease with myocardial insufficiency, severe renal or hepatic insufficiency, yellow fever vaccine) - Concomitant disease or severe uncontrolled clinical situation - Patients requiring long-term anticoagulant therapy - Thrombosis of the portal trunk or of a territory of 3 or more segments (or hepatofugal flow of the same territories) - Vascular involvement: 
 o severe atheromatous disease or, o collateral vascular pathways potentially endangering normal territories during embolization or, o arteritis of the branches of the hepatic artery to be treated or, o arterio-port or arterio-sus-hepatic fistula not embolisable by coils - Pregnancy or breastfeeding - Lack of effective contraception (for men or women of childbearing age) - Patient who for psychological, social, family or geographical reasons could not be followed regularly - Concurrent participation of the patient in another experiment
Study design and treatment plan	1 to 4 chemoembolisations (CHE) with idarubicin-loaded microbeads (100-300 μ m) (10 mg - Zavedos® Pfizer)

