For evaluation of response to treatment (primary endpoint), perform MRI 4-6 months after each HEC. **Except in the case of bilobar disease (for which 2 sessions of HEC should be scheduled upfront), retreatment (new HEC treatment) will be performed according to follow-up MRIs.** An MRI will be performed 4 to 6 weeks after each chemoembolization treatment. In case of tumor remnant or recurrence treatable by HEC (i.e., no portal trunk thrombosis or in a territory ≥ 3 segments, hepatopoitic portal flow, WHO status < 2 , no hepatic decompensation, no extrahepatic metastasis), a new course of HEC should be performed targeting the remnant or recurrence (same distinction as above: supra-selective OR lobar approach). In the absence of tumor remnant or recurrence on MRI performed 4-6 weeks, MRI surveillance is performed every 3 months and the modalities of retreatment are the same as before.

In all cases, MRI at 6 months from the date of inclusion must be performed (primary endpoint of the study).

At the end of the session, embolization with additional material is not recommended.

If in case of a single HEC, a recurrence of the disease is observed at the 3-month MRI, a second HEC can be performed and will be performed as part of the protocol.

V.3 Premedication and concomitant treatments

Sufficient hydration (up to 2 liters per day), adapted to the cirrhotic context, will be prescribed before and after chemoembolization for at least 48 hours.

In case of nausea or vomiting, provide adequate treatment according to center procedures.

After the procedure, level 1 to 3 (WHO) analgesics will be used in an appropriate dose.

At the end of the procedure, the pain felt by the patient will be recorded using a visual analog scale (VAS rated from 0 to 10). If VAS > 3, titration of IV morphine by an IDE according to the recommendations.

Any treatment required for patient comfort will be prescribed at the discretion of the investigator. The use of a preventive anti-emetic treatment is recommended.

VI. EXPECTED TOXICITIES AND DOSE ADJUSTMENT

VI.1 Chemoembolization

The main adverse effects expected with chemoembolization are:

- Unwanted reflux or passage of microbeads into normal arteries adjacent to the targeted lesion or through the lesion to other arteries or arterial beds
- Non-targeted embolization
- Pulmonary embolization
- Ischemia in an undesired location
- Capillary bed saturation and tissue damage
- Rupture of a vessel or lesion and hemorrhage

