- Neurological deficits including cranial nerve palsy
- Vasospasm
- Deaths
- Re-permeabilization
- Foreign body reactions requiring medical intervention
- Infection requiring medical intervention
- Catheter tip clot formation and subsequent mobilization

Expected effects related to the embolization procedure (from CNIHM anticancer files November 2008)

- Fever, hypochondrial pain, vomiting
- Transient thrombocytopenia and liver dysfunction
- Increased transaminases (cytolysis)
- Local ischemic and septic manifestations (cholecystitis, hepatic infarction, hepatic abscess, digestive hemorrhage)
- Renal insufficiency
- Hematoma at the puncture site
- Acute lower limb ischemia

Adaptation for chemoembolization

The interval between chemoembolization sessions should be 6 weeks plus or minus 1 week. Any additional time must be agreed upon by the coordinator.

HEC Session Rehearsal:

The chemoembolization session(s) are scheduled every 6 weeks, plus or minus 1 week.

The imaging technique, after each session, will be MRI and a cone beam CT acquisition (after 1^{ière} HEC for the translational study and after, if possible, each HEC to assess the quality of chemoembolization).

Subsequent sessions will be performed according to tumor response. No additional session is recommended in case of complete tumor response according to the modified RECIST criteria (mRECIST) (Appendix 2) or progression of a previously chemoembolized tumor.

In case of non-hematological toxicity of grade 3 or 4 attributable to HEC, no additional HEC is performed. In case of bleeding and/or severe liver failure and/or other toxicities secondary to a grade ≤ 3 chemoembolization session, the next session(s) will be performed at the discretion of the investigator.

Transient increases in ALT and/or AST in the 24-48 hours after HEC do not lead to failure to perform additional HEC. Indeed, this transient increase does not have a significant impact (R Sacco et al, Clinical impact of selective transarterial chemoembolization on hepatocellular carcinoma: A cohort study. World J Gastroenterol 2009 April 21; 15(15): 1843-1848).

VI.2 Idarubicin

The main effects expected for idarubicin (Zavedos® powder for solution for infusion) according to the current versions of the SPCs (version of 6/07/2006 appendix 8) are the following

- Significant spinal cord hypoplasia which can be responsible for serious or even fatal conditions
- Alopecia reversible on discontinuation of treatment

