### **7.4.3 Time to treatment failure**

#### **7.4.3.1 Definition**

It is defined as the time between the date of inclusion and the date of definitive cessation of treatment or death (whatever the cause). Patients without definitive treatment discontinuation and not deceased will be censored at the date of their last HEC.

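### Time to treatment failure makes no exception for stopping in complete response, so the best responders can be counted as failures, or censored, first

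*Protocol*

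**What the plan says.** **Event and censoring, protocol XII.2.2.** "Death, progression, and any discontinuation of protocol treatment (regardless of cause) are considered treatment failures". For the remainder: "Patients alive without failure will be censored at the date of the last 6-month morphological evaluation".

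**Event and censoring, SAP 7.4.3.1 under Time to treatment failure** (the same number recurs under Overall survival). The interval runs between "the date of inclusion and the date of definitive cessation of treatment or death (whatever the cause"). Progression is not named as an event. For the remainder: "Patients without definitive treatment discontinuation and not deceased will be censored at the date of their last HEC".

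**Treatment.** The synopsis plans "1 to 4 chemoembolisations (CHE) with idarubicin-loaded microbeads". For residual or recurrent tumour that can still be treated, protocol V.2.3 says that "a new course of HEC should be performed targeting the remnant or recurrence". Protocol VI.1 says: "No additional session is recommended in case of complete tumor response according to the modified RECIST criteria (mRECIST").

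**After a good response.** Under V.2.3, a patient with no residual tumour goes to MRI surveillance every 3 months and can be retreated on the same terms. A second session for recurrence after a single HEC belongs to the protocol treatment. The list of reasons for stopping in section VIII includes an investigator's decision, but names neither complete response nor completion of the sessions.

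**The concern.** An endpoint that treats every stop as a failure suits a treatment given until it no longer works. Here the number of sessions falls when the treatment works well and rises when tumour persists without progressing. If a stop in complete response is a failure, the endpoint partly measures how many sessions were needed, and early complete responders have the shortest times. If it is not a failure, the SAP censors these patients at the last HEC, so the censoring depends on response. Kaplan-Meier estimation, planned in SAP 7.4.3.2, assumes that it does not.

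Time to treatment failure is a named secondary objective, to be reported with medians, rates and confidence intervals. As the text stands, the result rests on a classification that neither document states. The two statisticians who program it independently (SAP 8.2.2) could classify the same patient differently.

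**Working it through.** The documents give no figure for this endpoint, so there is none to reproduce. The check is a timeline.

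**Inputs**
- First session 0 to 2 weeks after inclusion (protocol IV).
- Interval between sessions 6 ± 1 weeks, so 5 to 7 (protocol VI.1).
- MRI 4 to 6 weeks after each session (protocol V.2.3 and VII.2). One sentence in V.2.3 gives this range in months; I use weeks, as the same section and VII.2 do elsewhere.
- At most four sessions (synopsis).
- 1 month = 30.4375 days (SAP 6.2), so 6 months = 6 × 30.4375 / 7 = 26.1 weeks.

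**Complete response after session 1, no later session**
- Last HEC: week 0 to 2.
- MRI showing the response: 0 + 4 = 4 to 2 + 6 = 8 weeks.

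**Persistent, non-progressing tumour, four sessions**
- Fourth HEC: 0 + 3 × 5 = 15 to 2 + 3 × 7 = 23 weeks.
- MRI after it: 15 + 4 = 19 to 23 + 6 = 29 weeks.

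With the same start and the same dating convention, the two patients differ by 3 × 5 = 15 to 3 × 7 = 21 weeks. That is 15 × 7 / 30.4375 = 3.4 to 21 × 7 / 30.4375 = 4.8 months. In bilobar disease two sessions are planned from the outset, so the earliest such stop has its last HEC at 0 + 5 = 5 to 2 + 7 = 9 weeks.

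**The four readings for the complete responder who stays alive and progression-free**

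| Definition | Stop counts as an event | Stop does not count |
|---|---|---|
| Protocol XII.2.2 | failure at week 0-2 (HEC) or 4-8 (MRI) | censored at the 6-month evaluation, about week 26 |
| SAP 7.4.3.1 | failure at week 0-2 (HEC) or 4-8 (MRI) | censored at week 0-2 (last HEC) |

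Only the upper right cell credits the patient with the time spent in response. In the lower right cell, a responder who later dies keeps the full time to death, while one who remains well is cut back to week 0-2. The censoring time therefore depends on the outcome.

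**Illustration of how far the convention moves the result.** Assumptions, not taken from the documents: protocol definition, 25% progress at week 12, 10% to 40% are in complete response after session 1, and the rest finish their sessions by week 19. The failure-free proportion at 6 months is then:
- neither kind of stop counts: 100 − 25 = 75%;
- only complete-response stops count: 75 − 10 = 65% down to 75 − 40 = 35%;
- completion of sessions counts as well: 0%.

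SAP 4.6.1 reports 22 objective responders among 44 evaluable patients at the interim analysis. Responders are thus not a marginal group, but the share in complete response is not given.

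**The case against.** The strongest reply is that a complete responder has not discontinued anything. Under V.2.3 that patient is under surveillance and still eligible for protocol retreatment. VI.1 only advises against a further session, and section VIII lists neither complete response nor completion as a reason for stopping. Both censoring rules also presuppose that event-free patients exist. On the literal reading with completion counted too, the fourth session falls by week 23, before the 6-month evaluation, and the protocol's censoring rule would be nearly empty.

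This stands as far as it goes. It makes the protocol ambiguous rather than certainly inverted, although the investigator's decision in section VIII could cover a complete-response stop and XII.2.2 disregards the cause. It does not rescue the SAP, where the same lenient reading leads to censoring at week 0-2.

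A reader might infer more than the documents support:
- *Every patient has an event by design, and no time can exceed 29 weeks.* The censoring rules contradict the first part. Surveillance contradicts the second: after an MRI at week 4-8, 3-monthly MRIs fall at about weeks 17-21 and 30-34, and a recurrence found at the later one can be retreated.
- *Patients who complete all four sessions fail early.* They usually have persistent or recurrent tumour, and on the timeline they come last.
- *Complete responders always fail first.* A patient who progresses at the first MRI, or stops for toxicity after session 1, fails as early. The ordering holds only against persistent, non-progressing tumour.

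**Conclusion.** The point holds in this form: the definition of time to treatment failure does not say how to treat a stop for complete response or because no further session is needed, and the SAP's rule handles it badly whichever way it is read. Under the protocol the best responders can have the shortest times, by about 3.4 to 4.8 months against a patient treated four times, if the stop is classed as a discontinuation. Under the SAP, a complete responder after session 1 who stays alive and is not retreated contributes at most 0-2 weeks (censored, or an event dated at the HEC) or 4-8 weeks (an event dated at the MRI). Later failure-free time is lost in each case. Copying the protocol wording into the SAP would restore progression as an event and the later censoring date, but would leave the classification open.

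The figures assume the regular schedule without postponements. How much the reported curve would change depends on the number of early complete responses, which the documents do not give. The endpoint is secondary, descriptive and single-arm. Progression-free survival, overall survival and best response are reported separately, and the primary analysis and sample size are untouched. The correction is worth making but is not critical.

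**What to change.** Use one definition in protocol XII.2.2 and SAP 7.4.3.1:
- **Events:** death, progression, or stopping protocol treatment for toxicity, for patient refusal, or by an investigator decision other than for complete response or because no further session is needed.
- **Not events:** stopping in complete response or after the planned sessions. These patients stay at risk until progression or death.
- **Censoring:** patients without an event are censored at the last morphological evaluation, not at the last HEC.
- **Dating:** state which date marks a stop that counts, the last session or the assessment that led to the decision.

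This changes only the analysis definition, not how patients are treated. It costs a sentence or two in each document. One condition must be checked first: the definition needs the reason for stopping for every patient. The documents do not show that it is recorded. Section VIII lists reasons without saying they are collected, section XI asks in serious adverse event reports whether treatment was discontinued, and SAP 7.5.1 covers the cause of postponements. The observation book must be checked. SAP 4.6.2 describes the final analysis as still to come; the change should be dated and explained there, since the interim result was already known.
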